1.2 Therma-Scan System

First Sense Medical® has partnered with Therma-Scan Reference laboratory, an established pioneer in medical thermology. Therma-Scan has been in operation for over 40 years and operates a diagnostic clinical imaging facility in Birmingham, Michigan. [name] has developed a complex and inclusive protocol for the detection of tissue abnormalities indicative of Breast Cancer. He has examined thermology scans on more than 500,000 women using a medical grade digital infrared camera

¹Hoekstra P, The autonomic challenge and analytic breast thermology. *Thermology International*, 2004(14);3:106.

²[American Cancer Society](#)

that utilizes advanced imaging techniques. [name] follows an analytic technique derived from the Marseille system to provide results of a breast thermogram on a recognized 'TH' scale.

Breast thermology is effective on women of all ages. And the density of breast tissue is not an impediment to breast thermal analysis. Utilization of the Marseille system, an internationally standardized thermology classification system, defines 5 TH categories based on a range of breast thermal findings; these range from TH-1, considered normal, thru TH-5, considered abnormal. Additionally, there are two other categories: TH-0, a technically defective test and TH-6, a known biopsy proven cancer. Therma-Scan Reference Laboratory will screen for thermal signs indicative of change and report the findings using this proven system.

1.3 Sentinel Breast Scan® System [SBSII]

The SBSII will automate the recording of thermal data used in the Therma-Scan manual thermology protocol by utilizing a thermal camera sensitive to changes in breast temperature. The SBSII system uses a very sensitive thermography camera that detects and visually displays heat patterns that naturally emanate from the breast. SBSII captures this data digitally for subsequent analysis by Therma-Scan.

This study will evaluate the clinical efficacy of the SBSII device in patients completing a screening or diagnostic mammogram. The thermal images captured on examination will be analyzed by Therma-Scan and the results will be compared to mammographic analysis. If the Sentinel Breast Scan II findings indicate a reading of either TH4 or TH5, FSM may request that the patient receive additional testing, ie breast ultrasound or MRI. The additional testing that are not considered routine and necessary based on standard breast imaging, will be paid for by the sponsor, as outlined in the study budget.

1.3.1 Projected Advantages of Sentinel Breast Scan® Test/Therma-Scan System:

1. **Higher sensitivity and positive predictive value (PPV)**, Sensitivity measures the percentage of positive results when cancer is present. PPV is the true positive rate, and is the percentage of abnormalities with a positive result. The false positive rate is the percentage of normals identified as abnormal. Higher positive sensitivity in a screened population is the goal of all screening methods. This parameter will be utilized in the analysis of data from this study.
2. On average, mammographic **sensitivity** varies between 60-90%. It is lower in women under age 40 and in those with dense breast tissue.
3. **Year-to-year comparisons.** An important factor in analysis is identification of subtle visual change that is detected by comparing a previous mammogram to a current one. SBSII® seeks to identify subtle changes over time in breast thermal signals through the use of sophisticated software.
4. **Patient Safety:** Practice guidelines in the United States delay screening younger women with mammography based on the accretion rate of radiation exposure. Thermographic analysis of the breast is radiation free and innocuous as a screening modality for younger women and is not affected by breast density.

5. **Greater Access.** Because breast thermography can be performed in a non shielded environment, the opportunity to use this technology in a more welcoming environment is apparent.

Objectives/Purpose

The primary objectives of this feasibility study are to evaluate the functionality and performance of a novel adjunctive breast cancer screening system (FSM SBSII/Therma-Scan System) and utilize the data to provide further calibration for system software.

Specific Objective 1: To observe and document the performance of the FSM SBSII automated imaging system hardware and software in a clinical setting, and analysis of that data by TS.

Specific Objective 2: To both modify [if indicated] and measure the accuracy of an established manual thermographic analytical protocol (performed by TS), as well as define the approximate location of a particular finding and classify thermal irregularities in breast tissue.

Specific Objective 3: To develop and measure the accuracy of the system software to both approximate the geographic location of and classification of thermal change in breast tissue.

Thermal imaging captures the intensity and patterns of skin temperature using a high-performance infrared (8-14 μ m wavelength) camera. Pre-cancerous and cancerous breast tissue results in regional heating of the skin accompanied by complex irregularities in vascular patterns and aberrations in the adaptive modulation of skin temperatures³. This information can be imaged by thermal cameras and will be analyzed by TS. Although thermography cameras have been approved by the FDA for adjunctive use in breast cancer screening, this technology has not been widely accepted for several critical reasons. Lack of adequate quality control, adherence to standards for experience and training and inconsistency from practitioner-to-practitioner in the application of this technology have resulted in published studies with wide ranging sensitivity and specificity (Fitzgerald and Berentson-Shaw 2012). Because of this clinicians have been prevented from formulating a reasoned conclusion about the efficacy of breast thermography as adjunctive to standard breast imaging or its value as a method of risk assessment. Peer-reviewed clinical studies have amassed thousands of subjects and data points over time. However, a scarcity of systematic review and meta-analysis has impeded meaningful comparison to standard breast imaging technology (Vreugdenburg, Willis et al. 2013).

The core strengths of thermography are multi-faceted. Thermography is a fast, non-invasive, low cost and painless procedure performed without radiation exposure. Published studies support its use for early detection of breast tissue abnormalities and in identifying groups that may be at higher risk for developing breast cancer.

As an adjunct to mammography, thermography may be especially useful for screening younger, pre-menopausal women and women with dense breast tissue for whom mammography is less effective (Bleyer and Welch 2012).

³ Library, T.-S. R. (2011). "Thermology: Analytic Features." [A Professional's Guide To Breast Thermology](http://www.thermascan.com/professionals.html)
Retrieved January 4, 2013, from <http://www.thermascan.com/professionals.html>.

An automated platform for collecting thermal imaging data that provides objective, interpretative guidelines and standardized reporting would be an important adjunctive tool to aid in risk assessment and clinical decision-making in breast cancer screening.

Study Design and Selection and Exclusion of Subjects

1.4 Study Design: Testing a minimum of 2000 women receiving mammograms (comparing the SBSII/TS test results to the mammogram and biopsy results when applicable)

- a. SBSII test will be done before all mammograms, diagnostic or screening
- b. Women must wait a minimum of (3) days between mammography and the SBSII.
- c. If the SBSII test is positive and mammography is negative, FirstSense may request a breast ultrasound or MRI to determine the accuracy of SBSII. The acquisition order for MRI study will be done with prior approval by FSM.
- d. Any study subject, regardless of biopsy diagnosis and treatment, will continue to complete the SBS II imaging in conjunction with all future routine and necessary mammograms, not to exceed less than 6 months between each SBS II imaging, for up to 5 years from the start date of the subject's study participation. For subjects that undergo mastectomy after initial study participation, and are no longer completing routine and necessary mammograms, the SBS II will be completed with future routine and necessary breast MRI imaging, not to exceed less than 6 months between each SBS II imaging, for up to 5 years from the start date of the subject's study participation.

1.4.1 Subject Inclusion Criteria:

1. Female, over the age of 18 years of age.
2. Asymptomatic women or women who are being screened for breast abnormality.
3. Women scheduled for a mammogram or women who have had a mammogram and are given 3 days to wait in between their mammogram and scheduled biopsy and FS/TS system.
4. Not pregnant or breast feeding.
5. Signed Informed consent.

1.4.2 Subject Exclusion Criteria:

1. Subject does not meet inclusion criteria, noted above.
2. Use of 100 mg or more of niacin by tablet or niacin patch within the last 24 hours.
3. Use of nitroglycerin within the last 24 hours.
4. Subject experienced a fever of 102°F or higher within thirty-six (36) hours of the study.
5. Subject must not have had a mammogram, breast ultrasound, or breast exam within the last 72 hours prior to the SBS II.

1.4.3 Subject recommendations to follow prior to and day of Testing:

1. No use of tobacco within two (2) hours of study.
2. Subject should refrain from the consumption of caffeinated coffee, tea or any other caffeinated products for two (2) hours prior to the examination. This includes energy drinks/shots.
3. Subject should have no exposure to natural or artificial light for chest tanning, three (3) days or less prior to study.
4. Subject should have no exposure to vigorous physical stimulation, examination or compression of the breasts (self or clinical examination, ultrasound or mammogram) three (3) days or less, prior to study.
5. Subject should have no exposure to sauna, steam-room or hot/cold packs twenty-four (24) hours prior to the study.
6. Subject should have no evidence of new bruising, rash or skin irritation on the subject's breasts or underarms on the day of the study.
7. Subject will refrain from using deodorants, creams, powders or lotions that contain talcum powder which may cause an inflammation in the breast area on the day of the study.
8. Subjects exposed to outside environmental extremes, such as very cold or warm temperatures, should acclimate in a comfortable room temperature for approximately fifteen-twenty (15-20) minutes prior to the equilibration process.
9. The patient should refrain from exercise, bathing, or showering for one hour prior to examination.

These recommendations should be given to the patient prior to testing and then reviewed with them at their scheduled appointment. Should a patient not follow one of the recommendations, the study staff should note it on the CRF.

Study Procedure:

The study will initially involve approximately 2000 enrolled subjects. This number can be expanded with the consent of FSM and the principle investigator. The study will be led by the Principal Investigator (PI), [name]. The testing will be performed at the University of Toledo in Toledo, OH. The study staff or PI will speak with prospective women that have been referred to the University of Toledo by their physician, are patients of the University of Toledo, or are interested in becoming participants in this study. The study staff or PI will determine whether the patient is eligible to participate in this study and provide them the necessary documents to enroll. Women who have not been referred by their physician may still be considered for the study provided they are first determined to meet study eligibility requirements. The study staff will consent eligible participants using the IRB approved Informed Consent Form⁴. Each consented participant will be asked to fill out a questionnaire to provide pertinent medical information required by the protocol. This information will be utilized to determine study eligibility. The study coordinator will assign an arbitrary identifier for each participant enrolled in the study. The acquired study data and images will only be identified by the arbitrary identifier. Only the study staff and the PI will ever have access to both the participant name and the arbitrary

identifier.

Test Procedure:

Eligible participants will be consented using the IRB approved Informed Consent Form. Ineligible subjects will not be enrolled in this study. Study candidates will be given a questionnaire to complete. Once the questionnaire is completed by the potential participant, the study staff or PI will verify that the information is correct and complete and assess the participant’s study eligibility.

On the day of the study, the study staff will review the entire test procedure including safety precautions with the participant. The study staff will then begin the SBSII initialization procedure. The study staff will then assist the subject in preparation for the test. Subjects will be asked to disrobe from the waist up and sit in the chair facing the tester. Once the subject is positioned properly in front of the tester, the study staff will assure that the subject is comfortable and her arms are properly placed on the armrests.

With the subject properly positioned in front of the SBSII scanner, the study staff will inform the subject that the test will take approximately 7 minutes and that there will be no physical contact with the tester. The participant will be advised to remain still during the scanning process.

Before thermal image acquisition, the SBS II study staff operator will determine the frontal and lateral thermal image acquisition angles using the live thermal image of the subject’s breasts provided on the SBSII monitor. Once the angles are determined, the study staff operator will start the test. During the first step the patient will acclimate for 30 seconds, then cool air will be blown on the breasts for approximately 3 minutes. The air is then stopped and the patient will then acclimate for approximately 3 minutes. Thermal images are acquired starting at the first step and continuously until after the final acclimation step is completed. The patient must remain motionless throughout the initial period of acclimation, during the cool air sequence, and the final acclimation sequence in order to capture thermal images in series from the start of the test to its completion.

End of the test:

The test will be completed when the SBSII scanner signals that all images are acquired. The patient is now allowed to move.

Assessment of Safety and Risk

The potential risks are identified in this study and tests have been done to mitigate the risk.

Table 2. Risk Assessment

Medical Risk	Initial Severity	Initial Frequency	Control Measures	Final Severity	Final Frequency
Blowing cold air onto participants may cause discomfort.	Low	Remote	Participants may leave the study any time during a test.	Minor	Remote

Mix a patient's results with another patient.	Low	Remote	Each participant will be assigned a unique study ID. This ID will be entered electronically through the SBS II Tester User interface. This ID will be appended to the Thermal Data file names. Patients will not receive final reports.	Minor	None
---	-----	--------	---	-------	------

Discontinuation of the Study

At any time before or during the SBSII test, a subject is able to cancel or discontinue the clinical trial without penalty.

Data Analysis

1.5 Data analysis for Specific Objective 1:

The system hardware and software will be observed and log files will be analyzed by FSM to confirm proper operation of the system.

1.6 Data analysis for Specific Objective 2:

Thermal imaging data will be assessed by TS according to the internationally standardized thermology classification 'TH' scale, also known as the Marseilles system (Amalric, Brandone et al. 1978), which defines five categories of risk assessment.

The 3D, thermal and visible light data will be analyzed by TS to search for signs and criteria that indicate potential breast tissue abnormalities and arrive at a TH1-5 classification. Pattern recognition is used to identify blood vessels and measure the temperature points within these vessels. TS employs mathematical analysis to reduce the effective temperature variance and determine the probability of breast cancer. TS also uses mathematical techniques to measure magnitude of the focal areas on the breasts relative to the surrounding area. TS analyzes the average of approximately 10,000 data points and compares this analysis to the heat in any local hot spot. Sensitivity and specificity will be calculated by TS as described and data will be used to compare results with those from mammography and biopsy reports.

Clinically, a TH4-5 classification may result in a recommendation from the sponsor for further assessment. For study purposes, a comparison of the thermal categorization findings using the Marseille system to biopsy results will be analyzed. These results will provide a baseline for the semi-automated software analysis. Sensitivity and specificity will be calculated as follows:

TEST RESULT	CONDITION			Detection Rate
	Cancer	No Cancer	Total	
+ test	a (true positive)	b (false positive)	a+b	$\frac{a}{a+b}$ (positive predictive value=PPV)
- test	c (false negative)	d (true negative)	c+d	$\frac{d}{d+c}$ (negative predictive value=NPV)
Total	a+c	b+d	a+b+c+d	

\downarrow
 sensitivity = $\frac{a}{a+c}$

\downarrow
 specificity = $\frac{d}{b+d}$

In addition, the data collected will be used to train, test and measure the accuracy of risk assessments utilized in manual thermography analysis when a cold air challenge is introduced into the clinical examination procedure. All data collected from study mammograms and biopsies will be divided into a phases consisting of all unblinded exams resulting in the identification of up to 10 biopsy proven cancer cases, a testing phase consisting of all double blinded exams resulting in the identification of up to 45 biopsy proven cancer cases, and a double blinded clinical trial consisting of all exams resulting in the identification of up to 45 biopsy proven cancer cases to measure the accuracy of manual thermography analysis as stated in Specific Objective 2.

1.7 Data analysis for Specific Objective 3:

The accuracy of the imaging system software to define the approximate location and identification of aberrant thermal signatures of increased metabolic activity will be compared to results found on analysis of mammographic and biopsy results.

IRB Ethics & Informed Consent:

The protocol, Informed Consent Form, and relevant supporting information must be submitted to the IRB for review and must be approved before the study is initiated. In addition, any subject recruitment materials must be approved by the IRB prior to use. This study will be conducted in accordance with the ethical principles that have their origin in the Declaration of Helsinki and that are consistent with the International Conference on Harmonization - Good Clinical Practice (ICH-GCP) guidance and applicable regulatory requirements. The study will be conducted in accordance with the regulations of the United States Food and Drug Administration (FDA) as described in 21 CFR Parts 50, 56 and relevant sections of 21 CFR Part 812, and the IRB requirements.

The sponsor must submit any change to the protocol to the IRB for review and approval before implementation. A protocol change intended to eliminate an apparent immediate hazard to subjects may be implemented immediately, provided the reviewing IRB is notified within 5 working days of implementation.

It is the responsibility of the study staff or principal investigator to provide each subject with full and adequate verbal and written information, before inclusion in the study, using the IRB approved Informed Consent Form, including the objective and procedures of the study and the possible risks involved. Informed consent must be obtained prior to performing any study-related procedures, including screening. A copy of the signed Informed Consent Form will be given to the study subject.

Study Oversight & Clinical Trial Monitoring Plan:

Proper study monitoring ensures adequate protection of the rights of human subjects, the safety of subjects involved in a clinical investigation and the quality and integrity of the data submitted as a result of the investigation. Therefore, ongoing monitoring of this clinical research investigation will be conducted with the intent to:

1. Verify that patient consent for study participation has been properly obtained and documented ensuring compliance with Good Clinical Practice (GCP) standards and FDA regulations for protection of human subjects.
2. Verify that research patients entered into the study meet inclusion and exclusion criteria.
3. Verify that the study is conducted in compliance with the protocol.
4. Verify the accuracy and privacy of the data collected.
5. Verify that all essential documentation required by GCP standards and IDE regulations are present, current and appropriately filed.

Routine monitoring will be scheduled at appropriate intervals, with more frequent visits occurring at the beginning of the study. An initiation visit will take place, followed by routine monitoring visits. Additional visits can be scheduled at the request of the PI.

For each subject enrolled, there will be 100% monitoring of informed consent documents, inclusion/exclusion criteria, serious adverse events, and unanticipated adverse device effects. In addition, the first ten (10) subjects enrolled will have 100% of the data collection forms and associated source documents reviewed to ensure that all data collection has been completed and to ensure compliance with the protocol. FSM will need to receive copies of IC's or view them on site to verify they are properly signed by participant as well as the person who performed the consenting process.

Consent Forms

Review of the consent. The patient must sign the IRB approved version of the Informed Consent Form prior to initiation of the protocol.

- a. Verify that a signed and dated Informed Consent Form was obtained from every patient screened and that the study staff or principal investigator has signed all consents.
- b. Verify the date that the Informed Consent Form was signed is before any study-related activities were performed.
- c. Verify that the correct version of the Informed Consent Form was signed initially and that any subsequent versions of the Informed Consent Form which were approved during the time the patient participated in the study have also been signed.

Inclusion/Exclusion Criteria:

1. All inclusion/exclusion criteria must be met to determine subject's eligibility to enter the trial.
 - a. Verify that the study staff or principal investigator has signed a statement confirming patient eligibility.
 - b. Verify that there are no contraindications to the planned procedures.

Protocol Compliance:

1. Verify that the study is being conducted in compliance with the current IRB approved protocol.
2. Verify that the correct protocol version is in place.

AE/SAE Reporting:

1. Serious adverse events must be reported according to protocol requirements. All AE/SAE events will be monitored by and reported to [name], Quality Control Manager, First Sense Medical. An AE/SAE should be reported when any undesirable experience associated with the Sentinel Breast Scanner occurs, such as death, life-threatening event, hospitalization, disability or permanent damage, required intervention to prevent permanent impairment or damage to persons or device, electrical shock from the tester. Subjects should notify the study staff of any AE/SAE they believe should be reported. The study staff will then take all measures to ensure this is reported properly to the PI and First Sense Medical. Reports should be sent to the PI and [name], Quality Control Manager, First Sense Medical.
2. The following steps should be taken when reporting an AE/SAE:
 - a. Verify that the serious adverse event was reported within the proper time period.
 - b. Verify that a description of the AE/SAE, interventions, and outcome are described in the progress note and have been provided to the study staff.
 - c. Verify that a copy of the AE/SAE report and IRB notification are filed in the regulatory binder.
 - d. Verify that AE/SAE report(s) have been sent to the IRB/FDA, where required, and is filed in the regulatory binder.
 - e. Verify that the AE/SAE report(s) have been sent to the PI and [name], First Sense Medical.

UADE (Unanticipated adverse device effects) Reporting:

1. Unanticipated adverse device effects (UADE) must be reported according to protocol, IRB and FDA requirements.
 - a. Verify that an evaluation of the UADE was completed and that risk determination to subjects has been made.
 - b. Verify that investigations presenting an unreasonable risk were terminated within 5 days of risk determination and fewer than 15 days after receiving notice of such effect.
 - c. Verify that an evaluation of the UADE, interventions, and outcome are described in the report.

- d. Verify that the UADE report was sent to the IRB (and FDA, where required) within the 10 working day time period and that copies of such correspondence are filed in the regulatory binder.
- e. Verify that a copy of the UADE report, IRB notification, IRB and FDA response are filed in the regulatory binder.

Follow Up:

- a. FSM may collect follow up information about study subjects if the study subject completes additional testing related to breast screening.

Regulatory Binder:

The regulatory binder will be checked at each visit to ensure that all required regulatory documents have been obtained prior to the start of the study and have been kept current during the study. They include:

- 1. Protocol and protocol amendments
- 2. Sample, approved Informed Consent form
- 3. CVs for investigators and sub-investigators, if applicable
- 4. Copies of current licenses and or certifications
- 5. Sample CRFs
- 6. Subject master log/Subject screening log
 - i. Must show documentation of existence/participation of subjects
 - ii. Must be consistent with information within the CRF and in the individual subject record.
- 7. Serious Adverse Event log
- 8. IRB approval
- 9. IRB composition
- 10. IRB correspondence
- 11. Signature log
- 12. Delegation of Authority log
- 13. Visitor log
 - i. Monitor will sign and date the log indicating:
 - ii. Date of the visit
 - iii. Name of the individual conducting visit
 - iv. Coordinator will confirm that visit took place by initialing.
- 14. Correspondence related to the study

Source Documents:

Source documents are essential documents that individually and collectively permit evaluation of the conduct of a clinical study and the quality of the data produced. Examples of source documents are hospital records, office charts, lab reports, x-rays, case report forms when date is entered directly, magnetic media, and photographic negatives.

Specific case report forms in this trial will be considered source documents because the data are collected one-on-one with the subject and entered directly onto the case report form.

The files will be named with the inclusion of a blind patient ID. The patient name will not be in the filename or in the contained data. Only the study staff will know the relationship between the patient name and ID.

Data Management

The FSM will collect the following de-identified data during the study:

- 3-dimensional data providing shape and profile information of the patient's breast region.
- Thermal (infrared) images providing temperature information of the patient's breast and subclavian regions (near neck).
- Visible light images providing visual color and skin tone information of the subject's breast region.
- Log files providing information about SBS II.
- Completed patient CRFs (see below appendix)

This de-identified data will be stored on a secured cloud platform and in the SBS II hard drive and will only be accessible by Therma-Scan Reference Laboratory, LLC and First Sense Medical, LLC.

The files will be named with the inclusion of a blind patient ID. The patient name will not be in the filename or in the contained data. Only the study staff will know the relationship between the patient name and ID.

At Therma-Scan Reference Laboratory, LLC, the files will be stored on secured computers. Only selected TS employees trained in HIPAA and PHI protection regulations will have access to this data. Those employees will not know or have access to the subject's ID.

Intended Use of the Data:

The ID-protected, 3-dimensional, thermal and visible light data that will be collected by the SBS II will be analyzed by TS. The data will be analyzed and compared to mammography, breast ancillary tests, and / or biopsy findings, or follow up breast imaging. This protocol is used to search for signs and criteria that indicate the potential of breast tissue abnormalities associated with the risk of breast cancer. We intend to use this data solely for device development purposes. The log files will be analyzed by FS to confirm proper operation of the SBS II scanner. These results are not intended for submission to the FDA for marketing approval. These results are solely intended to be utilized to further develop and refine the FS/TS system and device performance. These results will not be utilized for any clinical decisions related to the subjects included in the study.

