PI	Principal Investigator
IRB	Institutional Review Board

Introduction

First Sense Medical®, LLC is a medical device company which has developed a breast cancer screening device, the Sentinel Breast Scan II [SBSII]. This radiation free device is being developed to produce data which will be analyzed by Therma-Scan Reference Laboratory. [name], CEO of Therma-Scan, is the author of a published paper based on breast thermal data with a reported 95% sensitivity and 91% specificity¹. The SBSII examination will take approximately 7 minutes.

This study is designed to evaluate the Sentinel Breast Scan II® as well as the analysis of data by Therma-Scan. SBSII® thermal breast data is an adjunctive aid to standard breast imaging. Currently, mammography is one of the standards of care in screening for visible signs of breast cancer. Breast thermology is the analysis of the heat signature data from an examined breast. All study costs will be incurred by the sponsor. Study subjects will incur no cost to participate. All scientific data revealed in this protocol will be used for the specific objectives of the study. The SBSII is a non-significant risk device. There is no contact with the subject during the entire procedure.

Background Information

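### Does calling PPV the true positive rate in section 1.3.1 endanger the accuracy analysis?

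*Protocol*

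**What the plan says.** Section 1.3.1, item 1, names higher sensitivity and PPV as a projected advantage of the system. It first describes sensitivity correctly: "Sensitivity measures the percentage of positive results when cancer is present". It then says "PPV is the true positive rate, and is the percentage of abnormalities with a positive result", and goes on to describe the false positive rate, also correctly, as a share of normal women. The item ends with "Higher positive sensitivity in a screened population is the goal of all screening methods", followed by "This parameter will be utilized in the analysis of data from this study".

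Section 1.6, on the analysis for Specific Objective 2, sets out a two-by-two table with a = true positives, b = false positives, c = false negatives and d = true negatives. Its margins give sensitivity a/(a+c), specificity d/(b+d), PPV a/(a+b) and NPV d/(d+c). The last column is headed "Detection Rate". The cells beneath it carry their own names, the first being "positive predictive value=PPV" and the second the corresponding label for NPV.

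**The concern.** Sensitivity conditions on disease: of those with cancer, how many test positive. PPV conditions on the test: of those who test positive, how many have cancer. Section 1.3.1 gives PPV the name of the first quantity, straight after defining that quantity correctly as sensitivity. Its words therefore conflict with the formula in section 1.6.

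The column heading in section 1.6 seems to compound this. A detection rate usually means the share of cancers found, or cancers found per woman examined. PPV is neither, and NPV counts women without cancer.

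Since item 1 also says that an unnamed parameter will be used in the analysis, one could fear that PPV would be computed with the wrong denominator, or that a predictive value would be reported as the share of cancers detected. Specific Objectives 2 and 3 are about measuring accuracy, so such a swap would matter if it happened.

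**Working it through.** The protocol attaches no computed PPV, sample size or error rate to this point, so there is no stated figure to reproduce. The check has two parts.

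**Definitions side by side (cells a, b, c, d from section 1.6)**

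| Measure | Words in 1.3.1 | Formula in 1.6 | Agreement |
|---|---|---|---|
| Sensitivity | positives among those with cancer | a/(a+c) | yes |
| False positive rate | normal women called abnormal, b/(b+d) | 1 − specificity = 1 − d/(b+d) = b/(b+d) | yes |
| PPV | called the true positive rate, i.e. a/(a+c) | a/(a+b) | no |
| NPV | not described | d/(d+c) | nothing to compare |

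The only conflict is the name given to PPV. For a > 0, a/(a+b) equals a/(a+c) only when b = c, so the two are not interchangeable. The second half of the PPV sentence is less clear-cut. Read on its own it describes sensitivity. Read in parallel with the sensitivity sentence before it, it can mean the share of positive results that are abnormal, which is PPV. The certain error is the term true positive rate.

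**How far apart the two measures can be (illustration only)**

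Inputs:
- N = 2000, the minimum in section 1.4.
- Sensitivity and specificity from the earlier paper cited in the Introduction: "95% sensitivity and 91% specificity".
- Cancers: the protocol gives no prevalence. Section 1.6 caps its first phase at "the identification of up to 10 biopsy proven cancer cases" and each of the two later phases at 45, so 10 + 45 + 45 = 100 if every cap is reached, or 100/2000 = 5%. Other prevalences are assumptions.

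At 5%:
- a = 0.95 × 100 = 95, and c = 100 − 95 = 5
- d = 0.91 × 1900 = 1729, and b = 1900 − 1729 = 171
- sensitivity = 95/100 = 95.0%
- PPV = 95/(95 + 171) = 95/266 = 35.7%
- NPV = 1729/(1729 + 5) = 1729/1734 = 99.7%

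Over a range of prevalence, by the same formulas:

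| Prevalence | a | b | Sensitivity | PPV |
|---|---|---|---|---|
| 0.5% | 9.5 | 179.1 | 95% | 5.0% |
| 1% | 19 | 178.2 | 95% | 9.6% |
| 2% | 38 | 176.4 | 95% | 17.7% |
| 5% | 95 | 171 | 95% | 35.7% |
| 10% | 190 | 162 | 95% | 54.0% |

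These figures show that sensitivity and PPV are different quantities. They do not show that the protocol would compute either one wrongly: every PPV above comes from the formula in section 1.6 exactly as printed.

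**The case for a change.** The strongest case for acting is that this is a contradiction, not a gap that a statistical analysis plan would fill. Sensitivity is in effect defined twice, once under the name PPV. The sentence sits beside a correct definition of the false positive rate, as if true and false positive rates were being presented as a pair, and PPV does not belong in that pair. The closing sentence of item 1 points to the analysis without naming its measure. With 35.7% against 95.0% in the illustration, a confused reader would be badly misled.

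Part of this stands. The term in section 1.3.1 is wrong and conflicts with section 1.6.

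The rest carries little weight:
- Item 1 is background. It sets no endpoint, threshold or sample size. Section 1.6 says how the accuracy measures are calculated, and the measures its introductory sentence names are sensitivity and specificity, not PPV.
- The column heading is loose, but the cells under it are correctly labelled. To take a detection rate from that column, a reader would have to ignore the name printed in the cell. The term is used nowhere else in the protocol and is not an endpoint.
- The unnamed parameter directly follows a sentence on sensitivity and most naturally means sensitivity. Section 1.6 defines both candidates correctly, so no result turns on the choice.
- The illustration treats upper caps as reached within a minimum enrolment, and pools an unblinded phase with two double-blinded ones. It is not a forecast.

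Rewording has a small hazard of its own. Subjects may be re-imaged for up to 5 years under section 1.4(d), and section 1.6 speaks of exams. A new definition phrased per woman for one measure and per test for another would bring in a unit of analysis that the table does not state.

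**Conclusion.** The slip is real but clerical: one wrong term for PPV in background text, and one loose heading over correctly named cells. The formulas that govern the calculation are right, so sensitivity, specificity, PPV and NPV all come out as they should, and no sample size, error rate or conclusion moves. The effect on computed results is zero.

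This rests on the analysis following section 1.6, which is what that section says will happen. The stakes are further limited because the section on intended use of the data reserves the results for device development and does not intend them for a marketing submission. Any protocol change must go to the IRB, and an amendment for this alone would gain nothing. The term can be tidied if the text is opened for another reason.
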